### **13.0 Provisions to Monitor the Data to Ensure the Safety of Subjects (if applicable)**

This Data and Safety Monitoring Plan (DSMP) has been developed in accordance with the National Institutes of Health (NIH) Office of Human Research Protection (OHRP) to assure the appropriate clinical safety monitoring of study subjects participating in this project.

**Summary of the Protocol.** The proposed Phase I project will develop and test a mobile technological system to be integrated into Prolonged Exposure (PE) treatment for posttraumatic stress disorder (PTSD). The investigative team will evaluate the usability, acceptability, feasibility, and preliminary efficacy of the system in civilians and US veterans or military personnel with PTSD. The primary outcomes of interest include self-report and clinician-administered PTSD severity scales.

**Trial Management.** The study will be managed from the Addiction Sciences Division within the Department of Psychiatry and Behavioral Sciences at the Medical University of South Carolina (MUSC), College of Medicine, Charleston, SC.

**Responsible Party.** [name] (PI) will be responsible for distinguishing between serious adverse events (SAEs) and non-serious adverse events (AEs), and determining initial study relatedness.

**Data and Safety Monitoring Board (DSMB).** We will create a DSMB to monitor overall participant safety, the rate and severity of adverse events, and the validity and integrity of the data. The panel will include 2 researchers with experience in treating patients with PTSD and a biostatistician. The board may be called at any point if needed for unexpected AEs, etc. Modifications will be made in the procedures and/or the protocol if necessary, based on the recommendations of the board. Confidentiality will be maintained during all phases of the study.

**Adverse Events.** An *Adverse Event (AE)* is defined as any unwanted change, physically, psychologically or behaviorally, that occurs in a study participant during the course of the study that may or may not be related to study participation. All AEs will be reviewed weekly by the PI, and annually by the DSMB, MUSC IRB, and VA Research and Development. A *Serious Adverse Event (SAE)* is defined as an adverse event that has one of the following outcomes: results in death, is life-threatening, requires inpatient hospitalization

or prolongation of existing hospitalization, results in persistent or significant disability/incapacity, is a congenital anomaly/birth defect, OR requires intervention to prevent one of the above outcomes.

**AE/Unanticipated Problem Follow-up.** Unanticipated problems, potential AEs and SAEs will be identified during the study via self-report data, as well as weekly assessments and interviews. All unexpected AEs and SAEs will be monitored until resolved. A detailed summary of all AEs will be prepared weekly by the research staff and reviewed by the PI at the weekly study team meeting.

**Risks of Study Participation.** Risks of participation related to inconvenience, psychological discomfort and boredom, physical discomfort, and confidentiality are outlined in the Human Subjects Section. Well-established strategies to protect participants against risks are also outlined.

**Safety Reporting.** AEs are reportable to the local IRB if the AE is unexpected AND related or possibly related AND are serious or more prevalent than expected. The IRB definition of *unexpected* is that the AE is not identified in nature, severity or frequency in the current protocol, informed consent, investigator brochure or with other current risk information. The definition of *related* is that there is a reasonable possibility that the adverse event may have been caused by the drug, device or intervention. SAEs will be reported within 48 hours of knowledge of the SAE. In accordance with the MUSC IRB, any deaths that occur during the study or 30 days post termination from the study will be reported within 24 hours, regardless of whether it is expected or unrelated. Follow-up of all unexpected and serious AEs will also be reported to the appropriate agencies. All AEs are reviewed weekly by the PI, and annually by the DSMB and IRB. Any significant actions taken by the local IRB and protocol changes will be reported to NIMH. An annual report summarizing all AEs will be provided to the NIMH project officer. This report will include 1) confirmation of adherence to the DSMP, 2) a summary of any data and safety monitoring issues that have arisen since the previous report, 3) a description of any changes in the study protocol or DSMP that might possibly affect risk, and 4) all new and continuing IRB approvals.

AEs and SAEs occurring during the course of study will be collected, documented, and reported in accordance with protocol and IRB reporting requirements. All research staff involved with AE reporting will receive training including identification, evaluation, documentation and reporting. All research staff will identify any potential AEs during the course of the study from self-report data and administration of assessments and interviews. This information will be provided to the PI, who will be responsible for AE/SAE assessment and evaluation including a determination of seriousness and study relatedness. Important medical events that may not result in death, be life-threatening or require hospitalization may be considered a serious adverse experience when, based upon appropriate medical judgment, they may jeopardize the participant and may require medical or surgical intervention to prevent one of the outcomes listed in this definition.

When a reportable SAE is identified, research staff will initiate an SAE form, and the following individuals will be notified within 48 hours of knowledge of the SAE: study co-investigators, the MUSC IRB, the NIMH project officer, and members of the DSMB, as appropriate. If complete information is not available when the initial 48-hour SAE report is disseminated, follow-up information will be gathered to enable a complete assessment and outcome of the event. This information may include hospital discharge records, autopsy reports, clinic records, etc. The research staff will attach copies of source documents to the SAE report for review by the PI and for forwarding to the NIMH project officer as appropriate.

**Study Safety.** Protocols for reported AEs and SAEs are outlined above. All unexpected AEs and SAEs will be monitored until resolved. A detailed summary of all AEs will be prepared weekly by the research staff. At the weekly team meetings (or before if urgent), the research staff will report any premonitory symptoms of clinical deterioration. Study procedures will follow the FDA's Good Clinical Practice Guidelines ([www.fda.gov/oc/gcp](http://www.fda.gov/oc/gcp)). Any outside requests for information or any breaches in confidentiality will be reported to [name]. All requests by participant's physicians and other medical providers will be

referred directly to [name].

**Follow-Up Phase.** All participants will be provided with a list of community resources upon study completion. Individuals presenting at any time with serious mental or physical health symptoms will be referred clinically for treatment. In the unlikely event that a participant demonstrates clinical deterioration, he/she will be referred clinically consistent with the procedures outlined in the Human Subjects section. In the event that emergency evaluation or intervention is necessary, the participant will be escorted by a study staff member to the psychiatric walk-in clinic or emergency room. Psychiatric hospitalization is available for emergencies at any point in the study.

**Data Management and Analysis.** A data analytic plan is outlined in the Statistical Analysis section. This study is powered to examine the efficacy of intelligent biometrics to optimize PE on the primary outcomes of interest. The main outcome variables include the severity of self-report and clinician-rated PTSD measures. Analyses will be guided by the specific hypotheses of the study and conducted by the study biostatistician. Post-hoc exploratory analyses will be conducted with two-tailed tests and more conservative statistical procedures which guard against Type I error (e.g., Tukey tests). All primary hypotheses will be tested at level of significance  $\alpha=0.05$ . We will also estimate the effect sizes of interest and provide 95% confidence intervals. Please see the Statistical Analysis and Power section for more details.

**Quality Assurance and Confidentiality.** Data quality will be monitored by random inspection of the completed forms by research staff and any irregularities or problems detected will be discussed with the PI. Project therapists will receive standardized training from the PI and Co-Is. Adherence to the manual will be monitored using session checklists and weekly supervision. If therapy drift is observed the therapists will be re-trained.

**DSM Plan Administration.** The PI will be primarily responsible for monitoring the study. The PI and a statistician will examine the outcomes database for missing data, unexpected distributions or responses, and outliers. A DSMB report will be filed with the IRB on a yearly basis, unless greater than expected problems occur. The report will include participant characteristics, retention and disposition of study participants, quality assurance issues and reports of AEs and SAEs. We will report main outcome results at the end of the trial. An annual report of all AEs will be submitted to the NIMH project officer. In addition, all AEs will be reviewed weekly by [name], and annually by the DSMB, local IRB and VA Research and Development. Any significant actions taken by the local IRB and protocol changes will be reported to NIMH.

For any SAE, the appropriate IRB-approved SAE protocol specific reporting forms will be completed and disseminated to the appropriate persons and within the designated timeframes as indicated above. If complete information is not available when the initial SAE report is disseminated, follow-up information will be gathered to enable a complete assessment and outcome of the event. This information may include hospital discharge records, autopsy reports, clinic records, etc. Follow-up of all unexpected and serious AEs will be reported to all regulatory entities including the local IRB, DSMB, and NIMH, as appropriate. For each AE/SAE recorded, the research staff will follow the AE/SAE until resolution, stabilization, or until the subject is no longer in the study.

**Stopping Rules for Clinical Trials.** The trial will be stopped under any of the following conditions: 1) there is clear evidence of harm; 2) there is no likelihood of demonstrating treatment benefit, or 3) there is overwhelming evidence of the benefit of treatment.

**ClinicalTrials.gov Requirements:** In accordance with Public Law 110-85, the proposed trial will be registered with ClinicalTrials.gov. Applicable requirements regarding results reporting will be adhered to.

## **14.0 Withdrawal of Subjects**

All participants will be screened thoroughly for eligibility following informed consent. The PI may discontinue participation at any time if a participant demonstrates or reports significant distress, presents a risk of harm to self or others, or is otherwise unable to complete the study. Participants may withdraw from participation at any time during the study procedure. Clinical referrals to community resources will be made available to all study participants.

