## 1.0 Objectives / Specific Aims

Posttraumatic stress disorder (PTSD) is a debilitating mental health condition that increases suicide risk and affects up to 20% of military veterans and 8% of the general population. Prolonged Exposure (PE) is a highly efficacious, evidence-based, cognitive-behavioral therapy for PTSD. However, dropout rates are high (25-30%) and an estimated one-third of patients who complete PE remain symptomatic. The primary objective of this study is to test a technology-based system that will (1) enable clinicians and clinical support staff to virtually accompany patients during in vivo exposures (IVEs) exercises to enhance engagement and successful completion of the exercises, and (2) provide clinicians and clinical support staff with real-time streaming of physiological biomarkers of affective engagement--galvanic skin response (GSR) and heart rate (HR)--and subjective units of distress (SUDS). This *actionable data* will be used in real-time by clinicians to modify the exercises and avoid under- and over-engagement, thereby minimizing inefficiencies and maximizing therapeutic value of IVEs. Secondary objectives are to use *passive data* collection to characterize IVEs, identify predictors of change, and inform next steps. To accomplish this, Zeriscope, a local small business with experience developing cutting-edge mobile technology platforms for health care, has partnered with clinical researchers at the Medical University of South Carolina (MUSC) to (1) develop a technology-based system to use intelligent biometrics (IB) to optimize PE ("IB-PE"), and (2) compare the guided IVE intervention to a passive data record-only version which will collect and store biometric and behavioral data for offline analyses. The following Specific Aim is proposed:

**Specific Aim:** **Conduct a 10-session randomized clinical trial (N=40 treatment-seeking veterans/civilians with current PTSD) to evaluate the acceptability and preliminary efficacy of IB-PE and investigate predictors of outcome.** Milestones: (1a) Evaluate ability of IB-PE (guided vs. record only) in reducing PTSD severity from baseline to session 10; and (2b) Use GSR, HR and SUDS to characterize IVEs and identify how each of these indicators predicts treatment response.

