**Prolonged Exposure (PE) Therapy.** PE will be delivered based on Foa's therapy manual (Foa et al., 2019). Specific to this study, participants will be asked to wear the apparatus during therapy sessions. During session 1, the Study Therapist will provide the rationale for PE, review trauma history, conduct breathing retraining, and orient the patient to the apparatus. Session 2 will include review of common reactions to trauma, introduction of SUDS, in vivo hierarchy development, instructions on how to use the IB-PE system, and a brief in-session practice. During the in vivo hierarchy development, participants will work with the study therapist to identify stressful triggers, listing these from most stressful to least stressful. The most stressful situation will be listed at the top of the hierarchy. A large part of PE therapy is safely exposing the participant to these individualized stressful situations (for example, going to a mall, walking in a crowded grocery store, visiting a park or engaging in a stressful activity, such as watching a suspenseful video clip). Part of the PE therapy includes going to these stressful situations as "homework" each week. That is, participants will be asked to expose themselves to their identified stressful scenarios outside of the office. Specific to this study, participants will be asked to wear the apparatus during these exercises. The exercises will be audio and video recorded. Sessions 3-9 include in vivo "homework" review

and planning for next in vivo assignments, imaginal exposure, and processing. During session 10, the therapist and patient review treatment progress and discuss potential next steps depending on each patient's needs (e.g., couple's therapy, vocational counseling). A participant may be offered the option of two additional sessions of PE (for a total of 12 sessions) if he or she does not demonstrate sufficient improvement of PTSD symptoms as determined by a decrease of 10+ points in PCL-5 score from Baseline to Session 9. All Study Therapists will have a master's or doctoral degree, complete a PE training, and attend weekly supervision during the trial. Sessions checklists will be used for fidelity to the manual (Carroll et al., 2007).

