**Assessments.** The instruments to be used were selected because many are standardized, have good psychometric properties, are widely used, and have been used by our research group. The primary outcome measures are described in this section. Information regarding additional measures can be found in Table 1.

Primary clinical outcomes include: the CAPS-5 for clinician-rated and PCL-5 for self-reported PTSD symptoms. The CAPS-5 is a 30-item structured diagnostic interview and gold standard for assessing PTSD (Weathers, Blake, et al., 2013). Independent evaluators blind to treatment condition will conduct the CAPS-5 at baseline, end of treatment, and follow up. The PCL-5 is a 20-item self-report measure that assesses PTSD severity each week and has excellent psychometric characteristics (Weathers, Litz, et al., 2013). IVE assessments include: psychophysiological reactivity (HR and GSR), which will be measured passively and continuously during IVEs using the patient worn data acquisition system (Zeriscope Inc.). Consistent with imaginal exposures, Subjective Units of Distress (SUDS; 0=no anxiety to 100=extreme anxiety) will be collected at 5-minute intervals during IVEs. A tone will signal patients to enter their SUDS using the device. Self-report questionnaires employed in our pilot feasibility study and other studies will assess comfort, acceptability, willingness to use, utility, and client satisfaction (Attikisson & Greenfield, 2004; Rizzo et al., 2010).

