**General Statistical Analyses.** All analyses will be performed on the intent-to-treat sample consisting of all randomized subjects. Baseline clinical and demographic characteristics will be collected and t-tests, chi-square tests, or their non-parametric equivalents will test for group differences, as appropriate, in SAS v9.4 (SAS Institute, Cary, NC, USA). Baseline characteristics that are associated with the primary outcome measures will be included as covariates in subsequent analyses. For all analyses, alpha will be set at 0.05. Urn randomization will be stratified by PTSD severity (CAP-5 total score at baseline). Based on our sample size and assuming 20% attrition (N=32), we have 80% power to detect a large effect (Cohen's  $d = 1.02$ ) for treatment outcome at a probability level of 0.05 for a two-tailed test (Cohen, 1988).

Hypothesis 1: IB-PE will be feasible and acceptable, as evidenced by at least 80% of participants (a) being able to turn on/off the equipment in  $\leq 5$  minutes; (b) reporting positive perceptions toward IB-PE via self-report assessments (Sekhon, Cartwright, & Francis, 2017). Hypothesis 2: Participants in the IB-PE guided group will evidence significantly greater pre- to post-treatment reductions in PTSD severity as compared to the record-only group. To test this hypothesis, independent generalized linear mixed effects models will be used to examine PCL-5 and CAPS-5 scores at final session by group. Models will be adjusted, respectively, for baseline PCL-5 and CAPS-5. Group will be entered as the predictor variable. Hypothesis 3: Higher levels of physiological and subjective engagement will predict greater treatment response. To test this hypothesis, mean HR, GSR, and SUDS responses during IVEs will be calculated according to previously published methods (Norholm et al., 2016; Rauch et al., 2018; Rothbaum et al., 2014) and multilevel modeling (MLM) will be used to analyze these variables as predictors of CAPS-5 at final session within and between treatment groups.

Exploratory analyses will examine group differences in the number of sessions required to attain significant symptom improvement on the PCL-5 from baseline (Rothbaum et al., 2014) and durability of effects at 1-month follow up. Data from both groups will be harnessed to explore the development of patient-specific algorithms predicting optimal engagement during IVE.

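### The protocol does not require outcome assessment after Prolonged Exposure stops, so early leavers may have no post-baseline CAPS-5 and drop out of a comparison promised for everyone randomized

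*Combined protocol and SAP*

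**What the plan says.** Section 14.0 gives the PI's authority as "The PI may discontinue participation at any time if a participant demonstrates or reports significant distress". It adds danger to self or others, and any other inability to finish, as grounds. Participants may also leave at will. The only thing offered afterwards is clinical referral. The rule is about participation as a whole, and assessment after PE stops is not mentioned.

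Section 10.0 (Assessments) sets the CAPS-5 schedule: "Independent evaluators blind to treatment condition will conduct the CAPS-5 at baseline, end of treatment, and follow up". Table 1 agrees. It marks CAPS-5 at baseline, Post TX and 1 month, leaves it blank for sessions 1-9, and has no early-termination column. PCL-5 is weekly.

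Section 11.0 (General Statistical Analyses) states: "All analyses will be performed on the intent-to-treat sample consisting of all randomized subjects". For Hypothesis 2, "independent generalized linear mixed effects models will be used to examine PCL-5 and CAPS-5 scores at final session by group", each adjusted for its baseline score. The power statement opens "Based on our sample size and assuming 20% attrition (N=32") and claims 80% power for d = 1.02.

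Section 1.0 places the endpoint at session 10: "Evaluate ability of IB-PE (guided vs. record only) in reducing PTSD severity from baseline to session 10". Section 13.0 says of the yearly DSMB report: "The report will include participant characteristics, retention and disposition of study participants". It does not ask for these by arm or by who decided to stop.

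**The concern.** Calling the analysis intent-to-treat does not supply the data that it needs. The Hypothesis 2 model uses one outcome value per person, taken at the final session, with baseline as a covariate. Someone who stops PE at session 4 and is not recalled has a baseline CAPS-5 and nothing after it, so that person adds nothing to the treatment contrast.

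The people at risk of being lost are not obviously a random subset, because the PI's listed grounds include distress and risk of harm. If loss is related to outcome and differs by arm, the comparison of those assessed is biased. If leavers gain less from guidance than stayers, it describes people who remained in treatment rather than the effect of being assigned to guidance. With only about 10 record-only participants expected, two losses remove a fifth of the comparator. A CAPS-5 that was never taken cannot be recovered at analysis.

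**Working it through.** **1. The plan's own figures.** Inputs: N = 40 (Section 6.0), 3:1 allocation (Section 3.0), and 20% attrition, d = 1.02, two-sided 0.05 (Section 11.0). 40 × (1 − 0.20) = 32, which reproduces the stated N and leaves 8 without a final score. With 30 guided and 10 record-only, equal loss removes 6 and 2, leaving 24:8. By the noncentral t, power at d = 1.02 is 79.7% for 16:16, which matches the stated 80%, but about 68% for 24:8. That mismatch is a separate matter; 68% is the reference used below.

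**2. People who may need assessment off treatment.** Section 1.0 cites 25-30% dropout from PE: 40 × 0.25 = 10 and 40 × 0.30 = 12. This is treatment dropout, not a stated rate of missing outcomes.

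**3. What a leaver contributes if not recalled.**
- CAPS-5: baseline only, so the person is absent from the final-session model.
- PCL-5: baseline plus weekly values to the last session attended. If *final session* means session 10, the person is absent. If it means the last session attended, the person is included. Section 11.0 does not define the term.

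**4. Bias with no true effect.** If leavers score δ SD worse than stayers in both arms, the shift in the guided-minus-record-only difference is (record-only loss rate − guided loss rate) × δ. The documents give no δ; 0.5 to 1.0 is assumed.
- Equal loss rates: 0.
- 4/30 guided and 4/10 record-only: (0.400 − 0.133) × 0.5 to 1.0 = 0.13 to 0.27 SD, against guided.
- 8/30 and 0/10: the same size, toward guided.

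A simulation gives a similar range. It randomizes 30:10 with an assumed baseline-final correlation of 0.5. Within each arm, those with the worst values of a removal score are dropped, and that score has a set correlation with the final outcome. ANCOVA is then run on those retained (40,000 runs, Monte Carlo SE 0.002). Shifts are in SD; negative favors guided.

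| Removed, guided/record-only | Corr. 0.2 | Corr. 0.5 | Corr. 1.0 |
|---|---|---|---|
| 3/1 | −0.003 | −0.004 | −0.013 |
| 6/2 | −0.002 | −0.007 | −0.016 |
| 6/1 | −0.026 | −0.065 | −0.135 |
| 3/2 | +0.022 | +0.050 | +0.108 |
| 3/0 | −0.028 | −0.072 | −0.146 |
| 6/0 | −0.051 | −0.128 | −0.274 |
| 0/1 | +0.024 | +0.063 | +0.131 |
| 0/2 | +0.047 | +0.118 | +0.242 |

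At correlation 0, every shift is within 0.002 of zero. All the removal rates are hypothetical.

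**5. Gap between those assessed and all randomized, if there is a true effect.** Assume equal loss by arm and an effect of 1.02 SD in those assessed. Then the all-randomized effect = 1.02 × (1 − loss + loss × share), where share is the fraction of the effect that leavers carry. At 20% loss, share 1, 0.5 and 0 gives 1.02, 0.92 and 0.82, a gap of 0 to 0.20 SD. The gap scales with the effect: at 0.5 SD it is at most 0.5 × 0.20 = 0.10.

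**6. Power, unadjusted, for shares 1, 0.5 and 0.**
- Not recalled (24:8): 68%.
- All leavers assessed (30:10): 78%, 69%, 59%.
- Half assessed (27:9), with effect 1.02 × (24 + 3 × share)/27: 73%, 68%, 63%.

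With an assumed baseline correlation of 0.5, the figure is 80% for 24:8, against 88%, 81% and 71% for 30:10.

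**The case against.** The strongest reply is that the finding rests on silence. Neither Post TX nor the 1-month visit is made conditional on completing session 10. For someone who stops PE, treatment has ended, so the Post TX visit could be held then. Section 11.0 commits to everyone randomized, and the 20% attrition figure, being below the cited PE dropout, is compatible with some dropouts being assessed. This stands in part: a reader might infer that the protocol bars leavers from assessment, and it does not. But no text directs anyone to assess them. The consent pages are not available, so wording there cannot be excluded.

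Four other stronger readings are tempting and are not supported:
- *25-30% of outcomes will be missing.* That figure is PE dropout.
- *PCL-5 is lost in the same way.* That depends on the undefined final session.
- *Removal for distress tilts the result toward one arm.* The documents give no removal rates, by arm or overall. Section 15.0 says that temporary symptom increases are unrelated to staying in treatment or to later symptoms. That statement concerns mild to moderate increases, so it does not settle the matter for significant distress, but it gives no direction either.
- *Assessing leavers raises power.* It may lower it, and the 30:10 figures assume that every leaver is assessed.

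One may also say that a 40-person trial of preliminary efficacy need not go this far. Section 13.0, however, describes the study as powered for efficacy on its primary outcomes.

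**Conclusion.** The gap is real and should be fixed, with medium confidence. It is secure for CAPS-5, one of two primary clinical outcomes. As written, the protocol does not secure a post-baseline CAPS-5 for people who stop early, and the plan itself counts on about 8 of 40 having no final score. The CAPS-5 comparison is therefore likely to cover those assessed rather than all randomized.

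The size of the harm is not established. The range of 0.05 to 0.27 SD holds only under unequal loss with a removal-outcome correlation of 0.5 to 1.0, both assumed, and its direction is unknown. The near-zero result under equal loss assumes no true effect; if leavers gain less than stayers, the separate gap in step 5 applies even with equal loss. The case for acting is fidelity to the declared analysis population and protection against outcome-related loss.

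**What to change.** Add to Section 14.0:

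> Stopping PE, whether decided by the PI or the participant, does not end study assessment. Unless the participant withdraws consent for assessment or the PI judges it unsafe, the blinded CAPS-5, the PCL-5 and the Post TX forms are completed (telehealth allowed) at the time session 10 was planned, no later than week 10, and again at 1 month, with the usual payments.

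Add a matching note to Table 1. Record the reason for stopping and who initiated it, and report both by arm.

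**Cost.** A short amendment and consent wording, plus evaluator time. For 8 to 12 leavers at two visits each, this is up to 16 to 24 assessments with existing instruments, evaluators and telehealth. Payments are $30 + $50 = $80 each, counting Post TX as one of the 10 paid visits (an assumption): 8 × $80 = $640 to 12 × $80 = $960. A person who leaves after session 9 would receive $50 + 9 × $30 + $80 = $400, the maximum already planned.

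**Limits.** Some leavers will still decline, and how the remaining missing scores are handled is a separate matter.

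**A separate, secondary change.** Section 10.0 says "A participant may be offered the option of two additional sessions of PE (for a total of 12 sessions"). Fixing the Hypothesis 2 assessment at session 10 for these participants, before the extra sessions, would agree with Section 1.0. Any repeat assessment after session 12 is not in the cost above.
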